4.1.7 V4 visit

The V4 visit will occur 6.5 weeks after the V3bis (\pm 4 days).

The following assessments will be conducted:

- Physical examination and vital signs assessment, according to [Sections 4.2.1.2](#) and [4.2.1.5](#),
- Weight and calculation of BMI,
- 12-lead ECG ([Section 4.2.1.6](#)),
- Blood and urine sample collection for haematology, blood chemistry, and urinary analysis according to [Section 4.2.1.8](#),
- Query for changes in concomitant medications,

- Recording of AEs (if any),
- ALSFRS-R measurement,
- ALS-MITOS measurement,
- King's College score measurement,
- Bioelectrical Impedance Analysis,
- C-SSRS evaluation,
- Patient's completion of ALSAQ-40,
- SVC assessment,
- Sniff test⁸,
- ABG,
- International Normalized Ratio (INR) if CSF sampling is planned,
- Collection of blood, urine and CSF samples for biomarkers analysis according to [Section 4.2.2.3](#),
- Pregnancy test in WOCBP. In addition to tests performed at hospital visits, pregnancy tests will be performed at monthly intervals during treatment and until the end of relevant systemic exposure. If a positive result is detected with urine pregnancy test, a serum pregnancy test will be performed to confirm the results.
- Appointment for the next visit,
- eCRF recording of data collected.

4.1.8 FU visit – V-FU

The V-FU will occur 4 weeks (\pm 1 week) after V4.

The following assessments will be conducted:

- Physical examination and vital signs assessment, according to [Sections 4.2.1.2](#) and [4.2.1.5](#),
- Weight and calculation of BMI,
- 12-lead ECG ([Section 4.2.1.6](#)),
- Crystalluria analyses according to [Section 4.2.1.9](#),
- Blood and urine samples collection for haematology, blood chemistry, and urinary analysis according to [Section 4.2.1.8](#),
- Serum pregnancy test,

⁸ The sniff test is optional. It will be performed only in sites that have the equipment and resources to perform this test.

- Query for changes in concomitant medications,
- Recording of AEs (if any),
- eCRF recording of data collected.

4.1.9 Premature discontinuation visit

Patients who prematurely withdraw from the study for any reason (Section 5.3), should be scheduled for a final visit as soon as possible and no later than 4 weeks after the last IMP intake.

The following assessments will be conducted:

- Physical examination and vital signs assessment, according to [Sections 4.2.1.2](#) and [4.2.1.5](#),
- Weight and calculation of BMI,
- 12-lead ECG ([Section 4.2.1.6](#)),
- Blood and urine sample collection for haematology, blood chemistry, and urinary analysis according to [Section 4.2.1.8](#),
- Crystalluria analyses according to [Section 4.2.1.9](#),
- Query for changes in concomitant medications,
- Recording of AEs (if any),
- ALSFRS-R measurement,
- ALS-MITOS measurement,
- King's College score measurement,
- Bioelectrical Impedance Analysis,
- C-SSRS evaluation,
- Patient's completion of ALSAQ-40,
- SVC assessment,
- Urine pregnancy test in WOCBP,
- Sniff test⁹,
- ABG,
- International Normalized Ratio (INR) if CSF sampling is planned,
- Collection of blood, urine and CSF samples for biomarkers analysis according to [Section 4.2.2.3](#),
- eCRF recording of data collected.

⁹ The sniff test is optional. It will be performed only in sites that have the equipment and resources to perform this test.

4.2 SPECIFIC ASSESSMENTS

4.2.1 Measurements of the primary variable

4.2.1.1 *Safety assessment*

The safety will be assessed on the occurrence of AEs (including SAEs, TEAEs, AESIs (see [Section 7](#)).

Identified AEs will be characterised in relation to type, seriousness, incidence, severity, and relationship to study treatment. Safety will be monitored over the course of the study by a DSMB. The percentage of patients requiring dosing interruption or definitive treatment discontinuation due to toxicity will be recorded.

Abnormal laboratory values, vital signs, ECG and other objective measurements

Laboratory values ([Section 4.2.1.8](#)), crystalluria ([Section 4.2.1.9](#)), physical examination ([Section 4.2.1.2](#)), vital signs ([Section 4.2.1.5](#)), ECGs ([Section 4.2.1.6](#)) and other objective measurements will be collected in related pages of eCRF. In addition, any of the abovementioned should be reported as AE if assessed as clinically significant by the investigator and as SAE or AESI if it meets the corresponding criteria (see [Section 7.3](#)).

In the relevant page of the eCRF, a clinical diagnosis should be recorded rather than the abnormal value itself, if this is available.

4.2.1.2 *Physical examination*

A physical examination will be performed at each visit. It will include the examination of general appearance, skin, neck (including thyroid), eyes, ears, nose, throat, lungs, heart, abdomen, lymph nodes, and neurological examination. Height in centimetres (cm) will be measured at screening. Body weight (to the nearest 0.1 kilogram [kg]) will be measured in patients' underwear.

If indicated based on medical history and/or symptoms, additional exams will be performed. Information about all physical examinations must be present in the source documentation at the study site.

4.2.1.3 *Neuropsychological assessment*

In order to assess the presence of active psychiatric illnesses, including dementia, patients will undergo a neuropsychological evaluation during the screening visit. The investigator will conduct the visit and perform a basic neuropsychiatric evaluation. No formal tests will be required.

4.2.1.4 *C-SSRS evaluation*

Considering the stage of development of IFB-088 (phase 2 with limited safety data in healthy volunteers), suicidal risk will be evaluated at screening and throughout the study using the Columbia-Suicide Severity Rating Scale.

4.2.1.5 *Vital signs*

This will include temperature, systolic and diastolic arterial pressure and heart rate. Information about the vital signs must be present in the source documentation at the study site. Blood pressure and heart rate will be measured after the patient has rested for 5 minutes, in both supine position and standing.

4.2.1.6 *Electrocardiogram*

A standard 12-lead ECG will be performed in triplicates in a resting position. Prior to the recording the patient should be at rest for at least 5 minutes. The ECG printout will be reviewed by the investigator.

4.2.1.7 *Laboratory assessments*

Accredited local and central laboratories will be used for analysis of specimens collected at each visit, according to [Table 3](#). Analyses will include:

- Complete laboratory evaluations (hematology, biochemistry, electrolytes, liver function, renal function, urinalysis) for safety assessment,
- Biomarker assessment ([Section 4.2.2.3](#)),
- Pregnancy test,
- Crystalluria ([Section 4.2.1.9](#)),
- PK.

Laboratory values that exceed the thresholds of normal laboratory values must be commented by the investigator on source documents and respective patient's laboratory eCRF page.

For each visit, the drawn amount of blood, urine and CSF required is detailed in [Table 3](#).

Table 3 – Schedule and location of the blood, urinary and cerebrospinal fluid tests

Sample	Assessment	Screening	Baseline (V0)	V1	V2	V3	V3bis	V4	V-FU	Premature discontinuation	Bio bank	Quantity per visit	Laboratory
Whole blood (EDTA/lithium heparin tube)	Safety (haematology)	X	X*	X	X	X		X	X	X			Local
Serum (serum-separating tube)	Safety (electrolytes, biochemistry, liver function, renal function)	X	X* ^a	X	X ^{a a}	X ^{a a} ^a	X	X	X	X		20 ml	
Plasma (EDTA tube)	Biomarkers		X			X		X		X	X	20 ml	Central
Whole blood (PAXgene blood RNA tube)	Biomarkers		X					X		X	X	5 ml	Central
Plasma (lithium heparin tube)	PK				X							10 ml	Central
Plasma (lithium heparin tube)	Efficacy (arterial blood gases)	X				X		X		X		2 ml	Local
Urine	Safety	X	X* [†]	X	X	X		X	X	X		50 ml	Local
Urine	Crystalluria				X				X	X		50 ml	Central
Urine	Biomarkers		X					X		X	X	100 ml	Central
Blood/urine	Pregnancy test	X**	X***		X***	X***		X***	X**	X***		2 ml/1 ml	Local
CSF	Biomarkers	X						X		X	X	1.8 ml	Central

CSF: cerebrospinal fluid, EDTA: ethylenediaminetetraacetic acid, V: visit, FU: follow-up.

* If needed, based on investigator's judgement.

† Additional urine analysis (dipstick) at V0 + one week.

^a Additional blood sampling for creatinine measurement at V0 + one week.^{a a} Additional blood sampling for creatinine measurement and calculation of eGFR at V2 + 1 month.^{a a a} Additional blood sampling for creatinine measurement and calculation of eGFR at V3 + 1 month and V3 + 2 months.

** Blood pregnancy test at screening and FU visit (V-FU).

*** Urine pregnancy test on a monthly basis until end of exposure to study treatment.

4.2.1.8 *Blood and urine safety analysis*

Blood and urine safety analyses will be performed at each visit after screening, except at baseline (V0) unless required by occurrence of intercurrent event since screening. Blood will be drawn via a hypodermic needle inserted into a vein in the arm and collected in the appropriate tube(s), according to [Table 3](#). The patient must be fasting overnight from 22:00. Urine specimens will be obtained by providing participants with a collection cup and instructions for the collection.

Further details on blood and urine sample processing, storage and shipping procedures will be provided in the laboratory procedures manual (LPM) provided by the sponsor.

The following parameters will be assessed for safety assessment:

Haematology

Haematology will include count of red blood cells, haemoglobin, haematocrit, total white blood cells count, platelet count, and a differential count including neutrophils, lymphocytes, monocytes, eosinophils, basophils.

Biochemistry

Biochemistry will include glucose, total cholesterol, high-density lipoprotein (HDL) cholesterol and calculated low-density lipoprotein (LDL) cholesterol, triglycerides, C-reactive protein, troponin T, creatine kinase, and uric acid.

Electrolytes

Electrolytes will include sodium, potassium, chloride, bicarbonate, calcium, magnesium, phosphorus.

Renal function

Renal function panel will include creatinine, blood urea nitrogen, estimated glomerular filtration rate, total protein.

Liver function

Liver function panel will include total protein, albumin, total bilirubin, direct bilirubin, alkaline phosphatase (ALP), aspartate aminotransferase (AST), alanine aminotransferase (ALT), gamma-glutamyl transferase (GGT), lactate dehydrogenase (LDH).

According to section 4.4 of riluzole SmPC, ALT should be measured every month during the first 3 months of treatment, every 3 months during the remainder of the first year, and periodically thereafter. This monitoring should be performed more frequently in patients with ALT increase under treatment. Depending on the date when riluzole has been initiated and the kinetics of ALT, additional measurements of ALT might therefore be necessary.

Urinary analysis

It includes blood, leukocytes, pH, glucose, and proteinuria assessed by means of commercial urine dipsticks. In case of proteinuria ≥ 30 mg/dL on the dipstick, 24-hour protein is also performed.

Urinary analysis will also include measurement of beta 2 microglobuline or albumin-to-creatinine ratio in mg/g or mg/mmol, microalbumine, creatinine, and proteins, and cytobacteriological examination of urine (CBEU). All these analyses will be performed in a spot urine sample.

4.2.1.9 *Crystalluria*

Microscopic analysis of urine will be performed to investigate drug-related crystalluria. Sample of first-morning micturition will be collected at the V2 visit. The sample will be collected by the hospital staff if the patient has been hospitalised the day before (see [Section 4.1.4](#)), or by the patients themselves if they have spent the night outside the hospital. In this case, patients will receive a sterile dedicated container either on the day before the V2 visit when they go on site for the IMP administration for PK assessment, or at the end of the V1 visit for those who will take the evening treatment at home before V2. A sample of 50 ml will be frozen at -20°C and sent to a central laboratory that will perform microscopic analysis within 7 days after urine collection. Urine freezing should be done within 3h of collection.

Crystalluria will also be investigated at the V-FU visit or at the premature discontinuation visit if any. Urine will be collected when the patient arrives in the hospital for his visit.

4.2.1.10 *Pregnancy testing*

All female patients of childbearing potential will have to perform a blood beta-human chorionic gonadotropin (beta-HCG) testing at screening. For WOCBP, high sensitivity urine pregnancy test will be performed at baseline and repeated on a monthly basis during treatment and until the end of relevant systemic exposure, as well as in case of premature discontinuation and at any time if pregnancy is suspected (sensitivity 25 mIU/ml or more).

In case of pregnancy, collection of information is needed as described in [Section 7.8](#).

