The safety results from the phase I study are reassuring and no serious adverse reactions are considered expected by the sponsor for the purpose of expedited reporting of suspected unexpected serious adverse reactions (SUSARs). However, human safety data with IFB-088 are limited to the results of this first-in-human study on healthy volunteers. Since IFB-088 has never yet been tested in ALS patients, who may present with potential additional risk factors linked to their condition, a set of measures will be implemented in this study in order to minimise those potential risks, including i) Restriction of eligibility criteria to patients with no other serious illness(es) or medical condition(s) such as cancer, cardiac, liver, renal or haematological diseases, ii) Regular monitoring of safety laboratory and clinical AEs in all patients enrolled in the present clinical trial, since as with any new drug, there is a risk that unidentified or unexpected side effects may occur, iii) Definition, monitoring and specific reporting procedure for AEs of special interest (AESIs), iv) Implementation of a data safety monitoring board (DSMB) for periodic benefit risk assessment.

In preclinical studies, kidneys appeared to be the only affected organs in Sprague Dawley rats at IFB-088 doses above the NOAEL (1.5 mg/kg/b.i.d., i.e. 3 mg/kg/day). Adverse, dose-related crystal nephropathy was observed in both sexes, but at slightly lower doses in males compared to females and was the first cause of moribundity and death. No signs of crystal nephropathy were reported in dogs and rabbits at dose levels of up to 16 mg/kg/day (i.e. 8 mg/kg b.i.d.) and 24 mg/kg/day (i.e. 12 mg/kg b.i.d), respectively. In the phase I P188 study no changes in the renal-associated biochemistry parameters and no IFB-088 related AEs from the renal system organ class were reported. Although the renal findings in the Sprague Dawley rat strain are not completely understood yet, the current data suggest that it likely represents a species-specific toxicity not representative of the risk in humans. Nonetheless renal toxicities will be reported in this study as AESIs and renal function will be closely monitored, along with microscopic examination of urine to detect crystals.

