Potential biomarkers known to be associated with the evolution of the disease and potentially modulated by IFB-088 treatment will be assessed before and during study treatment. Blood, urine

and CSF samples will be collected for this assessment (see [Table 3](#)). Further details on blood, urine and CSF sample processing, storage and shipping procedures will be provided in the LPM provided by the sponsor. Frozen samples will be kept in a biobank for further analyses (see [Section 4.2.2.5](#)).

Blood biomarkers

Blood will be collected in 2 different types of tubes to measure potential biomarkers in both plasma and whole blood (messenger RNA [mRNA], microRNA [miRNA]). Blood should be first drawn in Ethylenediaminetetraacetic acid (EDTA) tubes and then in PAXgene Blood RNA Tube, as described below.

Plasma

Blood for plasma biomarkers assessment will be collected at V0, V3 and V4 according to schedule of activities ([Sections 3.7](#) and [4.1](#)) in 2 tubes of 10 ml containing EDTA properly labelled with patient identification. After processing, plasma will be aliquoted in and stored at -80°C pending analyses. Samples will be stored at a facility designated by the sponsor. The following parameters will be analysed at a laboratory approved by the sponsor:

- NfL light chain: at baseline and 6 months,
- NfL heavy chain: at baseline and 6 months,
- TDP-43: at baseline and 6 months,
- Inflammation biomarkers (interleukin [IL]-6, tumour necrosis factor- α [TNF α], interferon γ [IFN γ], IL-1 β , IL-8, IL-10, monocyte chemoattractant protein-1 [MCP-1], nerve growth factor [NGF], brain-derived neurotrophic factor [BDNF], vascular endothelial growth factor [VEGF]), transforming growth factor beta [TGF β]: at baseline, 3 and 6 months,
- Oxidative stress biomarkers (reactive oxygen species): at baseline, 3 and 6 months.

Unused plasma aliquots will be kept in the biobank ([Section 4.2.2.5](#)) for potential further analyses.

Whole blood

For whole blood biomarkers assessment, blood will be drawn at V0 and V4 in PAXgene Blood RNA tubes. Tubes must be at room temperature prior to use and properly labelled with patient identification. The tube should be gently inverted 8 to 10 times and store at -80°C pending analyses. Samples will be stored at a facility designated by the sponsor and will be kept in a biobank ([Section 4.2.2.5](#)) for potential further analyses.

Urine biomarkers

Urine will be collected at V0 and V4.

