7.10 CLINICAL EVENTS RELATED TO ALS

Clinical events related to ALS or consisting in known ALS complications will be recorded in the AE section of the eCRF. When serious, these clinical events are exempt from SAE reporting, unless the investigator deems the event to be related to the administration of the study drug, or unless the event results in patient's death: in these 2 cases, the event should be reported as SAE. The following events will be considered clinical events related to ALS or ALS complications:

- Onset, changes or aggravation of speech and/or voice disorders,
- Onset, changes or aggravation of swallowing disorders including drooling, aspiration/choking,
- Onset, changes or aggravation of emotional disorders, including exaggerated and/or involuntary emotional responses, alteration and/or lack of control in emotive expression, fronto-temporal executive dysfunction,
- Onset, changes or aggravation of breathing difficulties,
- Onset, changes or aggravation of muscle and/or joint disorders and their consequences, including muscle weakness, muscle atrophy/wasting, muscle spasticity, muscle cramps, fasciculations, stiffness, joint pain and/or contractures, reduced dexterity, wrist drop, tripping, stumbling, awkwardness, foot drop, spasms, uncontrolled movements,
- Onset, changes or aggravation of upper and/or lower motor neuron signs and symptoms, including reflexes disorders (abnormal reflexes, hypo/hyperreflexia), abnormal motor nerve conduction studies.

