- Worsening (i.e. progression to a higher stage at 6 months compared to the baseline stage defined by ALS-MITOS score): the proportion of progressors will be compared between both treatment groups. The difference in binomial proportions will be estimated along with an exact 95% CI. A sensitivity Bayesian analysis using the historical placebo data from the ProMISe study [26] will be also performed and further detailed in the SAP. Progressors will also be analysed in a logistic regression model adjusting for treatment and additional relevant covariates (specified in the SAP). The treatment effect will be estimated in terms of an odds ratio associated with the 95% CI and p-value and also in terms of a difference in progression rates with its 95% CI using the method proposed by Ge and al. [45].
- Change in King's College score: the endpoint will be analysed with an approach similar to the analysis of ALS-MITOS score.

Analyses of the changes in efficacy endpoints from baseline to month 3 (as inferential analysis) and from month 3 to month 6 (as descriptive analysis) will be also proposed and further detailed in the SAP.

- Respiratory function: changes from baseline to 3 months and from baseline to 6 months will be analysed. Analyses will be further detailed in the SAP.
- Bioelectrical analysis: changes from baseline to 3 months and from baseline to 6 months will be analysed for the planned following parameters: phase angle, Z200/Z5 impedance ratio, skeletal muscle mass, dry mass, and dry mass without fat. Analyses will be further detailed in the SAP.

PK Analysis

Individual plasma concentrations of IFB-088 and IFB-139 (i.e. IFB-088 metabolite) with corresponding nominal sampling times, will be tabulated for each subject and scheduled sampling time, together with descriptive statistics. Mean plasma IFB-088 concentrations profiles by cohort will be presented over time graphically, using blood sampling time (x axis) and concentrations (y axis) on both linear and semi-log scales.

Derived and observed PK parameters will be evaluated by noncompartmental analysis. The following parameters will be listed and summarised by cohort, as appropriate:

- AUC, ng.h/mL,
- C_{max}, ng/mL, with associated T_{max}, h,

- Terminal or apparent terminal $t_{1/2}$, h,
- Apparent systemic clearance (Cl/F, L/h) and apparent volume of distribution (Vd/F, L) at steady state, where F is the overall oral bioavailability of IFB-088.

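### Creatinine and eGFR, the main blood markers of the kidney risk, drift with ALS muscle wasting, and the SAP does not use the placebo arm quantitatively to remove that drift

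*Protocol*

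**What the plan says.** Protocol 1.3 reports that "kidneys appeared to be the only affected organs in Sprague Dawley rats" above the no-adverse-effect level, and commits that "renal toxicities will be reported in this study as AESIs and renal function will be closely monitored", with urine microscopy for crystals.

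- **Blood at clinic visits (Protocol 4.2.1.8).** "Renal function panel will include creatinine, blood urea nitrogen, estimated glomerular filtration rate, total protein". No filtration marker independent of muscle is listed, and the eGFR equation is not named.
- **Extra draws (Protocol Table 3 footnotes).** "Additional blood sampling for creatinine measurement at V0 + one week"; "Additional blood sampling for creatinine measurement and calculation of eGFR at V2 + 1 month"; and the same pair at V3 + 1 month and V3 + 2 months. None includes blood urea nitrogen (BUN). The V3bis list in Protocol 4.1.6 has no filtration marker.
- **Urine (Protocol 4.2.1.8 and 4.2.1.9).** Dipstick, protein, microalbumin, and beta-2 microglobulin or an albumin-to-creatinine ratio. Crystals are examined at V2, then at V-FU or premature discontinuation.
- **Muscle.** Protocol 7.10 lists "muscle weakness, muscle atrophy/wasting, muscle spasticity" among ALS-related events. Protocol 8.1.5.2 plans impedance measures, "phase angle, Z200/Z5 impedance ratio, skeletal muscle mass, dry mass, and dry mass without fat", taken at V0, V3, V4 and premature discontinuation. SAP 5.11.6 only describes them, on the FAS.
- **Renal analysis.** SAP 5.12.3.3 gives shift tables against the normal range from baseline to V3 and V4, plus a summary of clinically significant abnormalities. SAP 5.2.22 and 5.12.1.2 add eGFR classes cut at 15, 29, 44, 59 and 90. Quantitative change from baseline in renal blood values goes to listings (SAP 5.12.3.2 and 5.12.3.3). Vital signs and ECG, by contrast, get change-from-baseline statistics (SAP 5.12.4.3 and 5.12.5.3).

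**The concern.** Serum creatinine reflects how much muscle produces as well as how much the kidney clears. That is general physiology; the documents do not state it. In a disease where wasting is expected, creatinine tends to fall and creatinine-based eGFR to rise for reasons unrelated to the kidney. A patient who loses both muscle and filtration can look stable.

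Safety is the primary objective and the kidney is the lead nonclinical risk, so the direction of this drift matters: within a patient it favours a reassuring reading. The trial has the natural control for it, a concurrent randomised placebo arm with the same disease. Shift tables by arm show that control only coarsely. They register a change only when a value crosses a limit, and they give no estimate of the difference between arms.

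**Working it through.** **The plan's own figures.** The only design figures concern SAEs, and the point does not depend on them. They reproduce: 1 − 0.95^28 = 0.762; 1 − 0.90^28 = 0.948; 42/0.85 = 49.4, rounded up to 50.

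**Coverage of renal draws on treatment.** Week 1, V1, V2, month 2, V3, month 4, month 5 and V4 make 8. Four (week 1, months 2, 4 and 5) have creatinine or eGFR only; the four clinic visits add BUN. Between V3 and V4, both renal draws are creatinine and eGFR only.

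**Masking within a patient.** Assume steady state, with creatinine proportional to production/GFR and eGFR proportional to 1/creatinine. With muscle loss m and true GFR loss g:

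creatinine relative to baseline = (1 − m)/(1 − g)

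The documents give no rate of muscle loss, so m = 5-15% over 6 months is an assumption.

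| m | GFR loss leaving creatinine unchanged | True GFR when eGFR reads 60 | Reading after a true fall from 90 to 72 |
|---|---|---|---|
| 5% | 5% | 57 | 75.8 |
| 10% | 10% | 54 | 80.0 |
| 15% | 15% | 51 | 84.7 |

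Larger losses remain visible. At m = 10%, a 30% GFR loss gives 0.90/0.70 = 1.29 (creatinine up 29%), and a 50% loss gives 0.90/0.50 = 1.80. At m = 15%, a 50% loss gives 0.85/0.50 = 1.70.

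Early draws are little affected. If 10% accrues linearly over 26 weeks, the drift is 10/26 = 0.4% at week 1 and 4 × 10/26 = 1.5% at week 4.

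**What the SAP tables register.** At m = 10%, a true fall from 90 to 81 reads 81/0.90 = 90, so no shift is recorded. Even without masking, a fall from 88 to 62 is (88 − 62)/88 = 30%, yet both values lie in the class between 59 and 90 and both are below the normal limit of 90 in SAP Table 4.

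**What a between-arm contrast does.** If both arms lose the same m and only the active arm loses g, the ratio of creatinine changes is [(1 − m)/(1 − g)]/(1 − m) = 1/(1 − g), and m cancels. For g = 10% this is 1.11, whatever m is. If instead the drug preserves muscle (say 5% loss against 10% on placebo) with equal GFR, the ratio is 0.95/0.90 = 1.056, a false kidney signal.

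**Precision.** With 28 and 14 patients, SE = SD × √(1/28 + 1/14) = 0.327 × SD. With t of about 2.02 and an assumed SD of log change of 0.10 to 0.20, the half-width is 0.066 to 0.132 on the log scale, or about 7% to 14%. The 11% contrast above (0.105 in logs) exceeds the half-width at SD 0.10 but not at SD 0.20.

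**The case against.** The strongest reply is that kidney safety does not rest on creatinine. BUN is in the panel. The rat lesion was crystal nephropathy, and the protocol looks for crystals directly. Dipstick blood and protein, microalbumin and a 24-hour protein test after a positive dipstick are also planned, and the AESI has no creatinine threshold. This stands, and it rules out a reading that some may be tempted by: that the plan monitors the kidney by creatinine alone, or that renal harm as a whole could go unseen. It does not close the gap. BUN is absent from the four extra draws, urine findings show injury rather than lost filtration, and for completers the second crystal sample falls about four weeks after V4.

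A second reply is that SAP 5.11.5 already lists creatinine among the biomarkers, expressed as log10 change to V3 and V4. The matrix is not named, the summary is descriptive, and it is on the FAS, so it cannot stand in for a safety comparison.

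A third is that randomisation already supplies the control. It does, but the planned tables do not turn it into an estimate.

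Two further objections stand in full. The 5-15% range is assumed, and the entry criteria (ALSFRS-R at least 36, symptoms for at most 18 months, very rapid decliners excluded) mean that heavy wasting is not a given. And a reader might infer that impedance muscle mass is the missing correction for creatinine. The documents do not support that: it is not scheduled at week 1, V1, V2 or months 2, 4 and 5, and change in muscle is a post-randomisation variable that treatment may affect.

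**Conclusion.** The point holds in limited form. Creatinine and creatinine-based eGFR are the main, not the only, blood markers of the lead kidney risk. Muscle wasting can partly mask small or late losses of filtration in a patient: of the order of 5-15% if muscle loss is 5-15%, on a steady-state assumption and with an unnamed eGFR equation. Losses of 30% or more stay visible on the same assumptions. The weakness in the SAP is that it reports these values in coarse categories and leaves change from baseline to listings, so the placebo arm is never used quantitatively to remove shared drift.

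This is an inexpensive improvement to a descriptive safety analysis. It is not an internal contradiction in the plan, nor evidence that harm has been or will be missed.

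**What to change.** Add to SAP 5.12.3.3, on the Safety Set:

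1. Change from baseline in log serum creatinine, and in eGFR, at V3 and V4: a summary by arm and a between-arm difference with 95% CI, adjusted for the baseline value.
2. Summaries of the same changes by arm at the interim draws. The SAP 5.12.3.2 note names V2 + 1 month, V3 + 1 month and V3 + 2 months for creatinine. It mentions V0 + 1 week only for the dipstick, so the week 1 creatinine should be added.
3. Change in impedance skeletal muscle mass by arm, shown alongside to aid interpretation. Any model adjusted for muscle change should be labelled exploratory, for the reason given above.

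**Cost.** One model per marker and visit, four fits in all, on data already collected. SAP section 5 requires approval before the blind is broken and provides for an addendum after database lock; an addition made after lock should be identified as such.

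**Downside.** The estimate is imprecise, a treatment effect on muscle would still confound it, and it does nothing for real-time detection in individual patients.

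**Optional, not part of the fix.** Protocol 4.2.2.3 says "Unused plasma aliquots will be kept in the biobank". Cystatin C could be run in one batch on V0, V3 and V4 samples from consenting patients, at most 50 × 3 = 150 assays; patients who declined storage would be missing.
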